### **Analyses for Aim 1**

The primary efficacy outcomes are amounts of breast milk expressed over the first 7 days post-initiation; days 14, 21, 28, 35, and 42 days post-initiation and weekly, and number of days to achieve lactogenesis stage II. To examine expressed breast milk amount over time (i.e. production of breast milk immediately after initiation and subsequently, volume measured daily over the first 7 days and on days 14, 21, 28, 28, and 42 post-initiation and weekly), we will compare the longitudinal profile of milk volume expressed in the three groups over the

study period using mixed effects models (MEM) analyses. These analyses will estimate the average change in breast milk volume within each group (early vs. immediate vs. late initiation) and individual change in breast milk volume for each mother. MEM analyses allow for missing data, measurement of study subjects at different time points during the study, and time varying covariates. MEM can also take into account the effect of clustering, i.e. correlation of repeated breast milk measurements within one subject (Hedeker & Gibbons, 2006; McCulloch & Searle, 2001). The efficacy variable expressed breast milk volume (mL) will be used as the dependent variable with treatment status (early vs. intermediate vs. late initiation), time and time-by-treatment interaction and gestational group (23-27 weeks vs. 38-32 weeks) as primary independent variables. In a second step, additional covariates will be included in the models to adjust for putative predictive variables such as age, mother's weight at delivery, diagnosis of preeclampsia or diabetes, parity, birth weight, weeks of gestation, behavioral factors including skin-to-skin contact ("kangaroo care"), lactation support and mean number of pumping attempts per day. Effect modifications of covariates will be examined through inclusion of a covariate-by-treatment interaction term in the multivariable models. For example, a significant age-by-treatment interaction would suggest that the relationship between treatment and milk volume is different for older mothers compared to younger mothers. Potential key intervening variables such as behavioral factors will be further examined using mediation analysis. Further, the relationship of maternal mood with amount of breast milk will be examined by inclusion of the MAACL-R scores obtained at discharge, days 21 and 42 in the longitudinal MEM model.

Additionally, unadjusted mean differences in volume of breast milk at day 1 through 42 will first be compared overall via one-way ANOVA (or equivalently non-parametric Kruskal-Wallis tests) between the three groups. Subsequently, pooled t-tests will be used to compare unadjusted means pairwise between the groups (using significance level  $\alpha = 0.02$  to account for multiple comparisons). Mean differences for volume of breast milk at day 1 through 42 and number of days to achieve lactogenesis stage II will be adjusted for gestational group (strata) and putative covariates such as age, mother's weight at delivery, diagnosis of preeclampsia or diabetes, parity, birth weight, weeks of gestation, behavioral factors including kangaroo care and lactation support. Mean number of pumping attempts per day will be compared for each outcome measure (as dependent variable) using a general linear model (GLM) approach for the three milk initiation groups.

Furthermore, survival distribution for time from delivery to lactogenesis stage II will be obtained for each group using the Kaplan-Meier product limit method, and will be compared using the logrank test. Cox proportional hazards regression modeling (PHM) will be used with time from delivery to lactogenesis stage II as the dependent variable, and treatment (early vs. moderate vs. late initiation) and gestational group (strata) as the primary independent variables. Additional covariates and interaction terms will be added as described above for MEM analyses.

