## **Potential Risks**

Milk expression procedures for mothers in this study will be the same as if they were not in the study; therefore, there is no more risk for participants than there would be in day-to-day life. If lactation problems occur, including nipple pain, problems with the mechanical pump, or breast discomfort, this information will be communicated to a lactation consultant in the Neonatal Intensive Care Unit. Infants' involvement will be purely observational, and therefore there is no risk added by their inclusion in the study.

In this study, the mothers will likely be expressing their milk earlier than standard clinical practice dictates. In our pilot work, mothers who initiated milk expression within one hour of delivery had less pain and stress associated with the initial milk expression session than those who began milk expression 1-6 hours following delivery. Therefore, those in the Intermediate and Late Expressers groups are more likely to experience discomfort. However, this discomfort is expected to be fleeting and no different than the discomfort the mother would have experienced in usual clinical care. It is important to note that initial milk expression will be facilitated only by the research coordinator, the PI, or a research assistant experienced with lactation. Ongoing lactation support will be the same for all lactating mothers in the NICU and will include lactation services and support by the nursing staff.

The PI will notify maternal subjects of new information that may become available and which might affect their decision to remain in the study. Because the subjects will be low-risk, the categorization of level of risk is minimal or the probability of harm or discomfort is not anticipated or greater than those encountered during the routine care. **Alternative treatments** include discontinuation of milk expression.

All documents will be de-identified using a subject number and filed within a locked filing cabinet within the PI's research space.

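### The covariate-adjusted Aim 1 models condition on behaviours that follow randomisation, and mean days to lactogenesis II has no behaviour-free comparison under Aim 1

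*Combined protocol and SAP*

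**What the plan says.** Mothers are randomised after the birth (Randomization). Pumping sessions, receipt of lactation assistance and kangaroo care are then logged, and the text below Table 2 says this is done so that they can serve as adjustment variables.

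Under Analyses for Aim 1:

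- **Volume, mixed model.** The first step contains treatment, time, their interaction and gestational group. Then, "In a second step, additional covariates will be included in the models". The list includes kangaroo care, "lactation support and mean number of pumping attempts per day".
- **Role of the behaviours.** The same paragraph states: "Potential key intervening variables such as behavioral factors will be further examined using mediation analysis".
- **Mean differences.** Volume is first compared without adjustment, by ANOVA and pairwise t-tests. Mean differences in volume and "number of days to achieve lactogenesis stage II will be adjusted for gestational group (strata) and putative covariates", among them "behavioral factors including kangaroo care and lactation support". No unadjusted comparison of mean days to lactogenesis II is described there.
- **Time to event.** Kaplan-Meier curves and a log-rank test come first, then a Cox model with treatment and gestational group. After that, "Additional covariates and interaction terms will be added as described above for MEM analyses".

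The sample size section powers lactogenesis II on an independent-sample t-test of mean hours, with no behavioural covariate.

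**The concern.** The Primary Aim asks how timing of first expression affects lactogenesis II and milk volume. In a randomised trial that is the total effect, including any part that works through what mothers do afterwards. If timing changes a behaviour that affects supply, a model holding that behaviour fixed answers a different question. Its estimate may be smaller or larger than the total effect.

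The documents suggest two possible links:

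- **Lactation support.** Potential Risks says "those in the Intermediate and Late Expressers groups are more likely to experience discomfort", and also "If lactation problems occur, including nipple pain, problems with the mechanical pump, or breast discomfort, this information will be communicated to a lactation consultant". The procedures say that NICU lactation services are given on request. Equal access therefore does not guarantee equal receipt, and receipt is what the log captures. If later groups receive more support and support raises supply, adjustment would exaggerate the benefit of early expression.
- **Pumping frequency.** Potential Problems and Alternative Strategies notes that women often give up pumping because they have little milk. Pumping can then be a consequence of supply, and adjusting for it can remove part of a real timing effect.

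For mean days to lactogenesis II, Aim 1 plans no clean comparison of means to set beside the adjusted one. The reader could not see whether adjustment had moved the result.

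**Working it through.** **1. The plan's own power figure.** Inputs from the sample size section: 60 per group, difference 34.1 h, SD 55.0 h, two-sided alpha 0.02, power 85%.

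- Effect size: 34.1/55.0 = 0.62.
- Noncentrality: 0.62 × √(60/2) = 3.40.
- Power: 85.8% by the normal approximation and 84.9% by the exact noncentral t (118 df). The normal formula needs 59 per group.

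The stated 85% is reproduced. It belongs to an unadjusted comparison of means, that is, to the total effect.

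**2. Which Aim 1 analyses are free of behavioural covariates.**

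| Outcome | Behaviour-free | Behaviour-adjusted |
|---|---|---|
| Volume | First-step mixed model; ANOVA or Kruskal-Wallis; t-tests | Second-step mixed model; adjusted mean differences |
| Lactogenesis II, time to event | Log-rank; first-step Cox | Extended Cox |
| Lactogenesis II, mean days | None described | Adjusted mean differences |

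Pumping frequency is explicit in the mixed model and enters the Cox model by cross-reference. Its place in the mean-days model is unclear, because the sentence on it is hard to parse. Kangaroo care and lactation support are explicit there.

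**3. What adjustment would do under stated assumptions.** In a linear model with no unmeasured common cause of behaviour and outcome,

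adjusted effect = total effect × (1 − mediated share).

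The totals are the sample size section's detectable differences, 125 mL (SD 250) and 34.1 h (SD 55), taken as absolute sizes. The shares are assumptions. A negative share stands for the lactation-support link above.

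| Assumed share | Volume | Time to lactogenesis II |
|---|---|---|
| −20% | 150 mL | 40.9 h |
| 0% | 125 mL | 34.1 h |
| 20% | 100 mL | 27.3 h |
| 50% | 62.5 mL | 17.05 h |

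A simulation with 60 per group and 6,000 runs gave mean adjusted coefficients of 150.6, 124.5, 99.2 and 61.8 mL, and 40.9, 34.1, 27.1 and 17.2 h. The unadjusted difference stayed at 124–126 mL and 34.0–34.2 h. This confirms the algebra but is not evidence about the shares.

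**4. How far apart the arms must be in behaviour.** Assume that one SD of behaviour moves the outcome by 0.3 SD. The required difference is share × total / (0.3 × SD outcome).

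- Volume: 20% needs 25/75 = 0.33 SD; 50% needs 62.5/75 = 0.83 SD.
- Hours: 20% needs 6.82/16.5 = 0.41 SD; 50% needs 17.05/16.5 = 1.03 SD.

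**5. Power for the adjusted contrast in hours.** With the SD left at 55 and the exact t, shares of 10%, 20%, 30% and 50% give 76%, 64%, 51% and 26%, against 84.9% for the total effect.

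**6. The adjusted estimate need not be a direct effect either.** Take assumed standardised paths: arm to behaviour 0.3, behaviour to outcome −0.3, direct effect −0.3, an unmeasured common cause with effect 0.5 on behaviour and −0.5 on outcome, and unit residual variances.

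- Total effect: −0.3 − 0.3 × 0.3 = −0.39.
- Fitted slope on behaviour: −(0.3 + 0.25/1.25) = −0.5.
- Adjusted treatment effect: −0.39 + 0.5 × 0.3 = −0.24.

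That equals neither the total effect (−0.39) nor the direct effect (−0.30).

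**The case against.** The strongest reply is that both primary outcomes already have behaviour-free analyses. The plan labels treatment, time and gestational group as the primary model terms, and behaviours enter only later. That stands, and it limits the consequence. But the label describes terms in a model. It does not say which analysis decides the outcome, and the section on multiple outcome variables sets alpha at 0.02 without naming one.

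Second, the lactogenesis II gap is narrow. The log-rank test and first-step Cox model cover the same event, and the reference to adjusted mean differences may presuppose unadjusted ones. Exploratory Aim 2 also plans an unadjusted comparison of mean time. The gap does concern only the comparison of means. However, the log-rank test and Cox model do not estimate the mean difference that was powered. The Exploratory Aim 2 comparison is split by gestation and omits the intermediate arm.

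Third, a behaviour-adjusted outcome model is a usual part of mediation analysis, which the plan schedules. That is a reason to place these models there, but the plan also uses them for adjusted efficacy estimates.

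Fourth, the link through discomfort is pieced together from separate paragraphs, and the shares are assumed. Both points are fair. The discomfort is expected to be fleeting, ongoing support is to be the same for all, and all mothers get the same pump, instructions and reminders. Large shares are therefore less likely, and no actual bias has been shown.

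**Conclusion.** The concern holds. The behaviours follow randomisation, and the plan itself regards them as possible mediators. Yet it adjusts for them in the second-step mixed model, the adjusted mean differences and the extended Cox model. Those estimates need not equal the total effect of timing. Mean days to lactogenesis II appears under Aim 1 only in behaviour-adjusted form, although an unadjusted comparison of means was powered at 85%.

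The size of any shift cannot be taken from the documents, and it is zero if timing does not affect the behaviours. The ranges of 150 to 63 mL and 40.9 to 17.1 h rest on assumed mediated shares of −20% to 50%, a linear model and no unmeasured confounding of behaviour and outcome. The behaviour-free analyses remain valid. This should be fixed before analysis, but it does not undermine the design.

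**What to change.** 1. Limit the covariate-adjusted Aim 1 efficacy models (mixed model, GLM, Cox) to variables fixed before randomisation: gestational stratum, age, weight at delivery, preeclampsia, diabetes, parity, birth weight and weeks of gestation.
2. Use kangaroo care, lactation support and pumping frequency only in the planned mediation analysis, or in association analyses labelled as non-randomised.
3. State that the first-step mixed model decides the volume outcome.
4. For lactogenesis II, add the comparison of mean time without behavioural covariates that the sample size section powers, and name one behaviour-free analysis as confirmatory. If that is the log-rank test or Cox model, say that the stated power figure does not refer to it.

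The cost is analysis-plan wording only. No data or participants are lost, the first-step models are already planned, and the mediation analysis already covers the behavioural factors.

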**Table 2. Instruments (Logs)**

Variable	Instrument	Measurement
Maternal Factors	Log maintained by Project Coordinator	Age, parity, diabetes, pregnancy induced hypertension, mode of delivery, type of anesthesia, experience with breastfeeding, smoking, obesity, antenatal steroids
Lactation Factors (1-3 below)		
1. Onset of lactogenesis stage II	Log maintained by Project Coordinator	Date and time of sensation of breast fullness Corresponding breast milk measurement
2. Milk volume	Log maintained by Project Coordinator	Daily total breast milk weight for days 1-7 24 hour sample weekly
3. Milk volume alternative for breastfed infants	Log maintained by Project Coordinator	(Test weighing) - difference in infant's weight before and after feeding as indicator of breast milk intake.
Behavioral Factors	Log maintained only by mother	Date and time of pumping sessions, episodes of lactation support. Kangaroo Care log will be maintained separately (see below).
Kangaroo care	Log maintained by nurse or mother	Incidence and length of kangaroo care in min.
Infant breast milk intake (1-2		

below)		
1. Weekly percentage of breast milk received by infant during first 6 weeks of life	Log maintained by Project Coordinator	Data extracted from medical record
2. Percentage of breast milk feedings at discharge	Log maintained by Project Coordinator	Data extracted from medical record

Mothers in all groups will be instructed to record daily in the Maternal Behavioral Factors log book the following data: number of expression sessions per day, the date and time of each pumping session, and whether they received lactation assistance (Appendix F). The frequency of milk expression will be verified by the research coordinator by documentation of the date and time of each vial of milk brought to the NICU. Kangaroo care is encouraged in this NICU and nursing protocols have been established to provide support to all mothers regarding provision of kangaroo care. Infants are also encouraged to suckle at the breast during kangaroo care. Episodes and duration of kangaroo care between mother and infant will be recorded on the Kangaroo Care log sheet (Appendix G) located at the infant's bedside by either the mother or the nurse. While control of these variables within the study is impossible, we will carefully document these behavioral factors to allow for inclusion in statistical analysis as adjustment variables.

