Beginning 24 hours after delivery and continuing daily, mothers will be questioned (either in person or over the phone) regarding a sudden feeling of fullness in their breasts as an indicator of the onset of lactogenesis II (Appendix H). This has been a traditional method of determining the timing of lactogenesis stage II and has been shown to correlate with actual timing of this stage (Chapman, Perez-Escamilla, 2000; Perez-Escamilla & Chapman, 2000). Due to the effects of anesthesia, post op pain, and pain medication, mothers may have difficulty appreciating indicators of the onset of lactogenesis stage II, we will therefore confirm the reliability of self-report by determining whether >100mL of milk is produced per a 24-hour period (Neville, Morton, & Umemura, 2001). Since it is anticipated the onset of lactogenesis stage II will occur during the first 7 days, the number of hours post-delivery until lactogenesis stage II will be captured and recorded by research team members in the Milk Volume log.

Prior to discharge, at day 21 and 42, mothers will be asked to complete the MAACL-R. The MAACL-R is a standardized instrument with well-documented psychometric properties that assesses mood states by using positive and negative mood states scales for Anxiety, Depression, Hostility, Positive Affect and Sensation Seeking. It consists of 132 adjectives that are at or below an 8th grade reading level and takes approximately 3 minutes to complete. This test has been successfully used by the consultant for this project in lactating mothers of premature infants (Hill et al 2006; Lubin and Zuckerman, 1999). Mothers will be phoned by the research coordinator the day before the scheduled testing day to remind them to complete the test. The written test that will be completed following discharge will be provided to the mothers upon study entry. Mothers will return the test when they visit their infant and results will be hand scored and recorded on the MAACL-R Result Log by either the RA or the research coordinator. The test and grading sheet will be purchased with institutional funds upon initiation of this project.

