## **Potential Problems and Alternative Strategies**

The most likely potential problem is difficulty retaining subjects in the study between consenting prior to delivery and initial breast milk expression. Although our pilot study indicated this dropout to be highly unlikely, to minimize this problem a member of the research team will be available to the mother to help her pump the first time (at the time designated). Should she chose to pump at a different time (earlier or later), then she will receive the standard care available to her from the nursing staff and will no longer be eligible for the study.

Another problem related to retention is the continued willingness of mothers to express milk at the frequency required and for the duration of the study (at least 5 times a day until attainment of lactogenesis stage II). While this frequency may appear burdensome, these are the standard directions provided to mothers of VLBW infants receiving standard care i.e. who are not enrolled in the study.

A third potential problem is retention of the mother in the study for 6 full weeks post-delivery, when many women stop pumping due to lack of breast milk. To encourage mothers to continue trying to express their milk, each mother will be assigned to a graduate research assistant with experience involving the care of lactating women. This same student RA will contact the mother three times per week, either in person in the hospital or via telephone. The student will remind the mother to continue to pump at least 5 times per day and to bring in her breast milk with every visit. The role of student RAs in maintaining contact with mothers will decrease the likelihood of contamination of data collection procedures, since the PI or one of the co-investigators could inadvertently provide lactation consultation during the calls.

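### The planned mediation analysis sets no time order between pumping behaviour and outcome, so a follow-up-long pumping mean could count low milk leading to less pumping as mediation

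*Combined protocol and SAP*

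**What the plan says.** All references are to the combined protocol and SAP.

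- **Mediation.** Analyses for Aim 1 gives it one sentence: "Potential key intervening variables such as behavioral factors will be further examined using mediation analysis". It names no outcome, mediator window, model or rule on time order.
- **The pumping variable.** The second-step covariates earlier in that paragraph list behavioural factors that end with "lactation support and mean number of pumping attempts per day". A per-day mean is the only form the plan gives for pumping, and its averaging period is not stated.
- **Cox model for time to lactogenesis II.** "Additional covariates and interaction terms will be added as described above for MEM analyses". The pumping mean therefore enters that model too.
- **Time-varying covariates.** The plan notes that "MEM analyses allow for missing data, measurement of study subjects at different time points during the study, and time varying covariates", but does not say that pumping will be handled in this way.
- **Data collected.** The text after Table 2 has mothers record "number of expression sessions per day, the date and time of each pumping session". It gives the purpose as adjustment: "we will carefully document these behavioral factors to allow for inclusion in statistical analysis as adjustment variables".
- **Timing of the event.** The procedures state: "Since it is anticipated the onset of lactogenesis stage II will occur during the first 7 days". Volume is followed to day 42.
- **Reverse path.** Potential Problems and Alternative Strategies describes the six-week period as one "when many women stop pumping due to lack of breast milk".

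**The concern.** A mediator has to come before the outcome it is meant to explain. A mean over the whole of follow-up does not meet that condition. For lactogenesis II, most of the mean would be recorded after the event. For milk volume, mediator and outcome would cover the same weeks, and the protocol itself says that low milk makes mothers stop pumping.

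If that feedback enters the mediator, part of the effect of early initiation could be credited to pumping frequency when frequency had only followed supply. The direct effect of early initiation would be understated by the same amount. The protocol hopes to influence unit practice, and whether timing works directly or through more frequent pumping bears on what units would change. This is a separate question from whether models of the total effect should adjust for behaviour at all.

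**Working it through.** The plan gives no figure for the mediation analysis, so there is none to reproduce. Three checks bear on the point.

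**1. How much of the pumping record falls after lactogenesis II?**
Inputs: onset within 7 days (procedures) and follow-up to day 42 (sample size section). The share of days after onset on day L is (42 − L)/42.
- L = 7: 35/42 = 83%.
- L = 2: 40/42 = 95%.

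If the mean covered only days 1 to 7, the share would be (7 − L)/7: 71% for L = 2, 43% for L = 4 and 0% for L = 7. The result therefore turns on a window that the plan does not state.

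The reverse path acts directly on a 42-day mean. As an illustration, a mother who pumps 5 times a day to day 21 and then stops for lack of milk has a mean of 5 × 21/42 = 2.5 a day.

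**2. Size of the bias if pumping only follows milk.**
Let Y = tX + u, where X is arm and u has variance s². Let M = gY + e, where e has variance v, so that pumping M has no effect on Y.
- Path from arm to mediator: gt.
- Coefficient of M in the regression of Y on X and M: g s²/(g² s² + v).
- Product: t × g² s²/(g² s² + v) = t × rho², where rho is the within-arm correlation of M and Y. The sign of g does not matter.

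The true mediated share is 0%. The reported share is 9% at rho = 0.3, 25% at 0.5 and 49% at 0.7. These values of rho are assumptions; the documents give none. On the plan's own effect sizes, with rho = 0.5:
- 125 mL of volume: 125 × 0.25 = 31 mL spurious indirect effect.
- 34.1 h to lactogenesis II: 34.1 × 0.25 = 8.5 h spurious indirect effect, leaving 25.6 h as direct.

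Simulation for lactogenesis II (60 per arm, two arms, 34.1 h, SD 55) agreed with these shares. A Sobel test at the plan's alpha of 0.02 was falsely significant in about 2%, 21% and 48–49% of runs at the three correlations. At 5% the rates were about 7–9%, 35% and 63–65%. The plan does not name the Sobel test.

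**3. A separate simulation for volume.**
Two arms of 60, effect 125 mL, SD 250 mL, 2000 runs. Assumed, not from the documents: lactogenesis II on day 3, pumping propensity 5 a day with SD 1, and post-onset pumping shifted by b sessions a day per SD of milk. Pumping has no effect on milk.

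| b | Spurious indirect effect, 42-day mean | Share of 125 mL | Both paths significant at 0.02 |
|---|---|---|---|
| 0 | 0 mL | 0% | 0% |
| 0.25 | 6 mL | 5% | 3% |
| 0.5 | 22 mL | 18% | 13% |
| 1.0 | 58 mL | 46% | 33% |
| 1.5 | 83 mL | 66% | 47% |

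This matches the formula. At b = 1 the feedback variance is (39/42)² = 0.862 and the remaining variance is about 1.02, so rho² = 0.862/(0.862 + 1.02) = 0.46. With the mediator restricted to sessions before onset, the indirect effect lay between −0.2 and 0.2 mL at every b. That is expected by construction, since the feedback in this model starts only after onset.

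**The case against.** Several stronger readings are tempting, and the documents do not support them.

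- **That the plan uses a study-long mean as the mediator.** It does not say so. No averaging period is given, and the mediation sentence refers to behavioural factors in general. Sessions are logged by date and time and the mixed model can take time-varying covariates, so a time-ordered mediator could be built. This stands: the fault is a missing rule, not a stated wrong choice. Even so, the per-day mean is the only pumping variable named, and nothing stops the analyst from using it.
- **That any pumping after lactogenesis II is invalid as a mediator.** The mediation sentence sits in the milk-volume paragraph and names no outcome. For volume on days 14 to 42, pumping after lactogenesis II but before the measurement can be a legitimate mediator. The 83% figure therefore applies only to the Cox model and to any mediation of lactogenesis II.
- **That the protocol concedes the reverse path for lactogenesis II.** Its remark concerns mothers who stop pumping during six weeks of follow-up. It supports feedback for later volume. It does not show that later onset lowers pumping frequency.
- **That false mediation of a known size will be reported.** The shares assume no true effect of pumping and attribute all the within-arm correlation to feedback, with correlations that have no source in the documents. They illustrate; they do not predict.

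Mediation is also a follow-up step, so nothing here touches the primary comparisons.

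**Conclusion.** The point holds in a conditional form. The plan sends behavioural factors to mediation analysis, gives pumping only as a per-day mean without a window, and sets no time order. It carries the same covariates into the Cox model and itself describes feedback from low milk to pumping. This is more than missing detail, because the one pumping variable named can carry information from after the outcome.

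If the mean is taken over 42 days, at least 83% of the diary days would post-date a lactogenesis II onset within 7 days, and feedback could be counted as mediation of volume. The bias could be nil or large: from 9% to 49% of the effect for correlations of 0.3 to 0.7, if pumping has no true effect. Because the defect is limited to secondary mediation and covariate-adjusted models, it should be corrected, but it does not threaten the main result.

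**What to change.** Amend the mediation sentence in Analyses for Aim 1 so that it names each outcome and requires the mediator to precede it.

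- **Milk volume.** Use pumping, kangaroo care and lactation support in the interval before each measurement. Earlier volume influences both later pumping and later volume and is itself affected by arm, so name a longitudinal mediation method that handles treatment-affected confounders. Simply adding earlier volume to a product-of-coefficients model would not recover the full indirect effect.
- **Lactogenesis II.** Use behaviour in a fixed early window counted from the first expression session, expressed as a rate, among mothers not yet at lactogenesis II when the window closes. Alternatively, use a time-varying covariate built only from sessions before onset. A window counted from delivery would not do. Arms start up to 6 hours apart, so a 24-hour window would give some late-arm mothers up to 6/24 = 25% less pumping time by design. The support visit, about 24 hours after the first session, would also fall largely outside it.
- **Exclusions and status.** Bar whole-study means from the mediation analysis and the Cox model, and label the mediation analysis exploratory.

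No new data are needed for pumping, since date and time are already logged; kangaroo care episodes and lactation assistance are recorded too. The cost is a few sentences, somewhat more programming for the longitudinal method, and a mediator measured over a shorter and noisier window.
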